#### VERSION DATE: 03/11/2021

Figure 1

5.2 Study Procedures: Participants will complete a baseline assessment (including a diagnostic interview, clinical assessments, behavioral tasks, questionnaires, an EEG/ECG visit, and an optional MRI scan) prior to intervention, an interim assessment (clinical assessments and questionnaires) after 5 intervention sessions, a post-intervention assessment (including clinical assessments, behavioral tasks, questionnaires, an EEG/ECG session, and an optional MRI scan) after the tDCS intervention, and a final assessment (clinical

assessments, behavioral tasks, questionnaires, and an EEG/ECG session) following the at-home/in-person MBT intervention. The intervention will consist of MBT completed at home or in-person and MBT completed in the laboratory concurrent with active or sham tDCS (see Figure 1 and Table 1 for an outline of study activities). All self-report questionnaires will be administered online through REDCap, a HIPAA-compliant survey system, or on paper. All online selfreport questionnaires administered through REDCap will be completed by participants either in-person or remotely. Participants who are unable to complete all online self-report questionnaires in-person due to time constraints will be emailed an access code for each questionnaire and a link to the REDCap website. Upon opening the website link, they will be prompted to enter their access code in order to fill out questionnaires. Questionnaires administered on paper will be entered into REDCap by research staff.

Remote Conduct of Study Procedures- In the interest of disease containment and prevention, study staff will use HIPAA-compliant communication platforms approved for use at the University of Minnesota (e.g., Zoom) at their discretion to conduct necessary study procedures when possible during the period of heightened public health concern due to COVID-19. This will allow for participants to be given the option for remote study visits when deemed necessary by either the participant or by research staff.

Week		1	1, 5, and 9	1 and 5	3-4	3	5	9
	Time	Baseline Assessment	EEG 1, 2, & 3	MRI 1 & 2	tDCS + MBT Visits 1- 10	Interim Assessment	Post-tDCS Assessment	Final Assessment
Consent		Х						
tDCS Safety Screen		Х						
MINI	20 min	Х						
MINI Depression Module							Х	Х
MADRS-S		Х				X	Х	Х
C-SSRS (LV or SLV)		Х				X	Х	Х
MAAS		Х				X	Х	Х
FMI		Х				Х	Х	Х
RSS		Х					Х	Х
IDAS-II		Х						
DAS		Х					Х	Х
DERS		Х					Х	Х
AAQ-II		Х					Х	Х

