- We will use a questionnaire to assess perceptions of tDCS treatment.

- Columbia-Suicide Severity Rating Scale (C-SSRS) assesses the presence and severity of suicidal ideation and behavior (Posner et al., 2011). The C-SSRS will be clinician administered with the participant by trained research staff and overseen by a licensed psychologist. Answers will be reviewed by trained clinical assessors who are supervised by a licensed psychologist. This will be administered at baseline for inclusion criteria, at the interim visit, at the post-tDCS and at final assessment visits to monitor suicidality.
- Inventory of Depression and Anxiety Symptoms (IDAS) assesses symptoms of depression and anxiety (Watson et al., 2007).
- Positive and Negative Affect Schedule (PANAS) is a mood scale that assesses positive and negative affect (Watson, Anna, & Tellegen, 1987). This will be administered at the beginning of each tDCS session and before and after each MRI and EEG session as a manipulation check and to assess participant mood at the end of the scans to ensure participants are not leaving sessions in a distressed mood. A study investigator will be contacted if the participant endorses a 5 ("Extremely") for being "upset," "guilty," "distressed," or "ashamed" at the end of the session.
- Dysfunctional Attitude Scale (DAS) assesses maladaptive beliefs associated with depression (Weissman & Beck, 1978)
- Action and Acceptance Questionnaire II assesses psychological inflexibility and experiential avoidance (Bond et al., 2011).
- Pittsburgh Sleep Quality Index (PSQI) assesses sleep quality (Buysse, Reynolds, Monk, Berman, & Kupfer, 1989).
- Cash Choice Task is a single-item survey assessing delay of gratification, impulsivity, and motivation (Wulfert et al., 2002).
- Participants will be asked at the beginning of each intervention session to rate the degree of rumination they experienced the day before. At the end of each MRI scan and EEG scan, participants will be asked to rate the degree of rumination they experienced during each scan (e.g.,

resting scan). They will rate the quality of mindfulness, rumination, neutral thinking, and rest, thoughts, and mood after respective EEG, MRI, and tDCS task completion.

- At the end of each intervention session and when they engage in MBT for the EEG and the MRI, participants will be asked to rate how successful they were at engaging in the MBT (see attached).

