**Suicide/Self-Injury Risk**: The population being researched in this study has a higher risk for suicidal ideation, suicide attempts, and serious injury due to depression. The research team will monitor depression (MADRS-S), suicidal ideation (C-SSRS), and self-harm behaviors (C-SSRS) at baseline, midway through the intervention assessments at the interim assessment, and post-intervention. Answers will be reviewed by the clinical assessor who is trained and supervised by a licensed psychologist. Participants who indicate suicidal ideation or significantly increased self-harm behaviors based on the C-SSRS will be asked to meet with one of the investigators of the study to assess risk.

Participants with suicidal ideation with no plan or intent who agree to a safety plan (either developed with the investigator or a pre-existing safety plan) will be allowed to continue in the study. The investigator will inform parents of the discussion and safety plan (if applicable).

Participants with severe self-harm (requiring stitches or

hospitalization), suicidal ideation with intent, or those who cannot or will not agree to a safety plan will be escorted to the Emergency Room located 1 floor below the Ambulatory Research Center (ARC) in the West Building of the Fairview Riverside Hospital.

**EEG/ECG:** Mild skin irritation may occur at the electrode placement site (e.g., redness).

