## 21.0 Setting

21.1 Research Sites: Potential participants will be recruited by flyers and advertisements posted around the University of Minnesota campus and surrounding local areas, including local clinics that allow research postings, and through the REP system. Clinical and behavioral assessments may be completed in the Department of Psychology, the Ambulatory Research Center, or at the Center for Neurobehavioral Development, or at the Department of Psychiatry

(Park Plaza) at the University of Minnesota. Stimulation and EEG/ECG visits will take place on the University of Minnesota, Twin Cities Campus, at [name] MRI scanning will take place at the Center for Magnetic Resonance Research (CMRR).

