Research related activities may also be conducted at the Center for Neurobehavioral Development (CNBD). The CNBD is a research center that supports research on brain development in relation to cognitive and behavioral development. The CNBD has research space as well as brain imaging equipment, tDCS equipment, and software. EEG and tDCS sessions may also be conducted at the CNBD.

[name] is a licensed child and adolescent psychiatrist with expertise in adolescent depression. [name] is a licensed psychologist who runs a practicum for clinical psychology trainees and will oversee clinical assessments and training in clinical assessments. Either [name] or [name] will be available to provide consult in the case of any adverse events. All study staff will complete appropriate IRB and institutional trainings.

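### The suicide-risk rule in 13.1 requires a physical escort to the Emergency Room, which cannot be carried out as written at the remote visits that 5.2 allows

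*Combined protocol and SAP*

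**What the plan says.** Section 13.1 (Suicide/Self-Injury Risk) sets three triggers: self-harm serious enough to need stitches or admission, suicidal ideation with intent, and inability or refusal to agree a safety plan. Participants with "suicidal ideation with intent, or those who cannot or will not agree to a safety plan will be escorted to the Emergency Room", as are those with the first trigger. The room is identified by its position: each such participant "will be escorted to the Emergency Room located 1 floor below the Ambulatory Research Center (ARC"). The section gives no other destination or procedure for these participants.

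The finding comes from the C-SSRS. Under Clinical Assessments in 5.2: "The C-SSRS will be clinician administered with the participant by trained research staff and overseen by a licensed psychologist". On timing: "This will be administered at baseline for inclusion criteria, at the interim visit, at the post-tDCS and at final assessment visits".

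Two other sections say where such assessments may happen. Section 21.1: "Clinical and behavioral assessments may be completed in the Department of Psychology, the Ambulatory Research Center, or at the Center for Neurobehavioral Development". A fourth site, Park Plaza, completes that list: "or at the Department of Psychiatry". Section 5.2, on remote conduct during the COVID-19 period using platforms such as Zoom: "This will allow for participants to be given the option for remote study visits when deemed necessary by either the participant or by research staff".

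The revision history shows Park Plaza added for clinical interviews in version 11 and the remote option added in version 13.

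**The concern.** The escort is written as something staff will do, and it attaches to the gravest results of the main suicidality measure in a depressed sample aged 17 to 24. The protocol itself describes this population as being at higher risk. The places and formats in which the measure may be given have since widened, but the action has not been adapted to them. If a participant on a video call reports intent, staff following 13.1 literally have an instruction they cannot perform. Nothing in the documents requires them to have established where that participant is. The participant may be a 17-year-old. What is at stake is participant safety and adherence to the protocol at the moment when both matter most. No estimate or test is affected.

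**Working it through.** There is no stated figure to reproduce. The check sets the provisions side by side.

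**1. Settings in which the C-SSRS may be given.** It is an interview listed among the clinical assessments, so 21.1 applies and names four in-person sites: the Department of Psychology, the ARC, the CNBD and Park Plaza. Sites other than the ARC: 4 − 1 = 3. Section 5.2 adds remote visits and names no procedure as excluded.

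**2. Can the 13.1 action be performed in each setting?**

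| Setting | Staff with the participant? | Escort possible? | Route stated in 13.1? |
|---|---|---|---|
| ARC | Yes | Yes | Yes |
| Department of Psychology, CNBD, Park Plaza | Yes | Yes, nothing in the documents rules it out | No |
| Remote visit | No | No | No |

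**3. Do other sections close the remote gap?**

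- 17.1 lets confidentiality be broken for active suicidal ideation.
- 17.2 has a licensed psychologist or supervising psychiatrist contacted in a clinical emergency to decide whether to intervene. It lists active suicidal ideation with a plan among incidents that need immediate intervention. Its requirement that staff constantly watch the participant covers stimulation sessions only.
- 18.1 recognises that staff may have to seek outside help when someone is in danger of serious harm.
- 6.0 keeps participant contact information, which is not the same as where the person is during a given call.

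The provisions in 17.1, 17.2 and 18.1 are not tied to a site, so staff at a remote visit are not without recourse. None of them says how a remote participant reaches emergency care, and none requires the participant's location to be known. Sending outside help depends on that location.

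**4. When the conflict could arise.** The C-SSRS is scheduled at four time points. The baseline administration comes before those who are actively suicidal with intent and plan are excluded (8.2), and the telephone-screen MADRS-S leaves out item 9 (8.3). The first full suicidality assessment can therefore be the one that triggers the rule.

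**The case against.** The strongest reply is that 13.1 describes a destination and does not confine the rule to ARC visits. At the Department of Psychology, the CNBD or Park Plaza a staff member is in the room and can accompany the participant. The documents give no distances or transport facts that would make this impracticable. That stands. A reader might infer that the rule works only at the ARC and fails in every other setting. The documents do not support this: for the three other sites they show an unstated route, not an unworkable rule.

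A second reply is that the remote premise is inferred. Section 5.2 limits remote conduct to necessary procedures, when possible, in the COVID-19 period, and it does not name the C-SSRS. This is fair as a limit on how often the conflict could occur. It does not remove the conflict, because the general wording covers the C-SSRS and remains in the current version.

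A third reply is that 17.1, 17.2 and 18.1 already let staff reach a clinician, break confidentiality and seek help. That also stands, and it rules out any reading that the plan is silent on remote emergencies. What remains is that these provisions do not replace the mandatory escort and do not ask for the participant's location.

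A reader might also try to count the assessments affected. Section 10.1 has 75 people undergoing the initial assessment and at least 30 completing, so planned administrations are roughly 75 + 3 × 30 = 165. The documents give no share done remotely, and nearly all of these would be routine interviews, not events that trigger an escort. Multiplying 165 by a guessed share would present routine assessments as failed emergencies.

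**Conclusion.** The concern holds in a limited form. In one setting, the remote visit, the action that 13.1 makes mandatory cannot be carried out as written. In three further in-person settings it can be, but the protocol does not state how. The general emergency provisions reduce the consequence without resolving the inconsistency.

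The conclusion rests on one reading: that the remote option in 5.2 extends to the C-SSRS because nothing excludes it. If the investigators intended the C-SSRS always to be given in person, the conflict disappears once the protocol says so. The documents do not show how many C-SSRS interviews were or would be remote, so no frequency is claimed. The point deserves correction because it concerns a stated safety rule and is cheap to put right.

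**What to change.** Reconcile 5.2, 13.1, 17.1, 17.2, 18.1 and 21.1 so that whatever action the protocol states can be carried out in every setting where the C-SSRS may be given. For the in-person sites this means stating the route. For remote visits it means either stating how the action is carried out or stating that the C-SSRS is not done remotely.

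If remote C-SSRS interviews are kept, add a logistical step: before the interview starts, staff record the participant's current location, a call-back number and an emergency contact (the parent or guardian for a minor).

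The risk thresholds, the clinical response and the arrangements for clinician availability are for the investigators to decide, and nothing here proposes a change to them.

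The cost is a short amendment, a few extra fields on the assessment form and one more contact detail to hold securely.

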#### MRI

- Acquisition: All participants meeting MRI criteria to participate in the study following the clinical interview will be scanned using a 3T Siemens Prisma MR system at CMRR. The MRI scan is optional, and participants may choose to complete other study-related activities without undergoing the MRI scan. The Prisma is a fully-clinical derivation of the Connectome MRI scanner developed by Siemens and UMN at CMRR for the WashU-UMinn Human Connectome Project. All participants will be scanned at baseline, and 1-2 business days following the last day of the tDCS intervention. Participants will complete MRI safety screening. High-resolution T1 and T2 images will be collected. We will also collect a *field map* to correct the fMRI data for the geometric distortion caused by magnetic field inhomogeneity. This will take approximately 15 minutes.
- The research team will utilize the CMRR Center's screening tools and adhere to the screening SOP during enrollment of all research participants in this protocol. The CMRR Center's screening tools and SOP are IRB approved under the CMRR Center's Grand (HSC# 1406M51205) and

information regarding screening procedures is publically available on the CMRR website (CMRR Policies/ Procedures).

- Resting State and Mindful Breathing Scans: Whole-brain T2\*-weighted functional volumes will be obtained during rest, with eyes open while viewing a fixation cross (12 min) and while practicing mindful breathing (12 min). The duration and the choice of fixation cross as the resting condition are selected to optimize reliability. The mindful breathing scan will only be conducted at the postintervention scan.
- Rumination Task: Participants will be instructed to think about a series of 30 statements (30 seconds each, interspersed by 10 seconds of fixation cross) that are designed to induce either rumination, non-ruminative abstract thinking, and non-ruminative concrete thinking (5 statements of a single category per block, after which participants rate the valence of their thoughts during the block and current feelings) (Cooney, Joormann, Eugène, Dennis, & Gotlib, 2010). This task will last approximately 20 minutes.
- Hariri Task: Participants will be asked to match angry or sad emotional faces or horizontal and vertical ellipses (Hariri et al., 2002). This task will last approximately 5 minutes.

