#### 8.0 Study Population

*8.1* Inclusion Criteria:

- Female, Aged 17-24 years old
- Diagnosis of major depressive disorder (MDD), Dysthymia, or Other specified/Unspecified Depressive Disorder based on MINI.
- Experiencing current symptoms of depression as indexed by a MADRS-S score  $\geq 13$
- Ability to access the MBT online-based application (e.g., on a personal laptop, tablet, or cell phone)
- Fluent in English
- *8.2* Exclusion Criteria:
  - Any participant with a current diagnosis of epilepsy (must be seizure-free during the 2 years prior to consent to be included)
  - Any participant with a clinically defined neurological disorder or insult indicating, but not limited to, a condition likely to increase the risk of seizure; such as, space occupying brain lesion; history of cerebrovascular accident; transient ischemic attack within two years; cerebral aneurysm; dementia; brain surgery; history of stroke
  - Any participant with an increased risk of seizure for any reason, including prior diagnosis of increased intracranial pressure or history of significant head trauma with loss of consciousness for ≥ 5 minutes.
  - Participants with active or inactive implants (including device leads), including deep brain stimulators, cochlear implants, and vagus nerve stimulators
  - Participants with pre-existing sores or lesions at the site of tDCS or EEG electrode placement
  - A hair style that would impede EEG and tDCS electrode contact (e.g., dread locks)
  - Any participant with a current or possibility of current pregnancy
  - Participants unable to give informed consent.
  - Participation in any investigational drug trial within 4 weeks of the baseline visit

- Clinically significant laboratory abnormality or medical condition, that in the opinion of the investigator would hinder the participant in completing the procedures required by the study
- Currently actively suicidal with intent and plan determined by the C-SSRS at the baseline visit.
- A diagnosis of current or recent substance use disorder (within the past 12 months)
- A diagnosis of Schizophrenia, Bipolar Disorder, or Autism
- Unstable psychotherapy (therapy must be for at least 3 months prior to entry into the study, with no anticipation of change in the frequency or treatment focus of the therapeutic sessions over the duration of the study)

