- 13.2 Reproduction Risks: The effects of tDCS, EEG and MRI scans on the unborn fetus are not known, and participating females should not be pregnant. Pregnant participants will not undergo the stimulation, EEG or MRI scans. Participants and parents if participants are under the age of 18 will be told that the participant should not undergo study procedures if there is a pregnancy or possibility of a pregnancy. Participants will be informed about pregnancy risks during the consent process and will be encouraged to use a reliable form of birth control. Participants will take a mandatory pregnancy test before each MRI scan. If the urine pregnancy test is positive, the participant will not undergo the MRI scan or any tDCS sessions. If the pregnancy test is positive at the post-tDCS session, participants will not undergo the MRI scan but may choose to complete the 3-week at-home / in-person MBT training and clinical assessments. Participants will be asked to inform study staff at any other point of the MRI and tDCS visits if they have any concerns that they may be pregnant. Additional pregnancy tests can be offered at any point during other visits. Pregnancy and toxicology screens will be conducted at the CMRR by research staff. Participants will provide urine samples and we will use a pregnancy test strip (Clarity Diagnostics; Manufacturer # DTG-HCG100) to test for pregnancy and an Integrated E-Z Split Key Cup Urine Drug Screening with Adulteration for 5 Drugs for the toxicology screen (Manufacturer # DUD157023019). Both of these tests have a CLIA waiver (see attached materials for more details on the tests and for CLIA waiver documentation). These tests will be purchased through UMarket. Results will be recorded on CRF forms for MRI scanner sessions. Urine will be disposed of by being flushed down the toilet and used testing materials will be disposed of in the garbage.
- *13.3* **Risks to Others**: There are no anticipated risks to others who are not participants.
- 13.4 Email Risks: Participants will be able to opt in to communicating with study staff via unencrypted email to arrange their appointments and receive study instructions. There are risks associated with email communication, and these risks increase when the emails are sent without an encryption

service. Risks of sending or receiving emails without encryption include, but are not limited to:

- Others can intercept messages.

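### The only required pregnancy test is attached to the optional MRI, so a participant who has no scan needs no test before her ten tDCS sessions

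*Combined protocol and SAP*

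**What the plan says.** Three parts of the protocol bear on this.

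- **The rule on exposure.** Section 8.2 lists among its exclusions "Any participant with a current or possibility of current pregnancy". Section 13.2 says that the fetal effects of the study procedures are unknown and states: "Pregnant participants will not undergo the stimulation, EEG or MRI scans". It adds the consequence of a positive result: "If the urine pregnancy test is positive, the participant will not undergo the MRI scan or any tDCS sessions".
- **The testing.** Section 13.2 makes one kind of test compulsory: "Participants will take a mandatory pregnancy test before each MRI scan". Beyond that, "Additional pregnancy tests can be offered at any point during other visits", and participants are asked to tell staff if they are concerned that they may be pregnant. On place and record, "Pregnancy and toxicology screens will be conducted at the CMRR by research staff" and "Results will be recorded on CRF forms for MRI scanner sessions". In the schedule of activities in section 5.2, the pregnancy test has a single mark. It lines up with the MRI 1 and 2 column, beside the MRI safety screen, the urine toxicology screen and the anatomical scan.
- **Who is scanned.** The MRI subsection of 5.2 says: "The MRI scan is optional, and participants may choose to complete other study-related activities without undergoing the MRI scan". Section 5.3 also calls the scan optional. The MRI exclusion criteria in section 8.2 keep people who cannot be scanned in the rest of the study.

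**The concern.** The bar on stimulation covers every participant, but the required check on it covers only those who choose, and are able, to have a scan. Everyone enrolled is female and aged 17 to 24. The sponsor treats pregnancy as a reason to withhold tDCS and a urine strip as a way to detect it, so one would expect the strip to be tied to the stimulation. It is tied instead to a different and optional procedure. At stake is an undetected early pregnancy exposed to stimulation whose fetal effects section 13.2 calls unknown, in a participant for whom no step of the plan was missed.

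**Working it through.** The documents give no figure to reproduce. The check is a count of required tests along the visit sequence.

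**Inputs**
- Baseline EEG/ECG is visit 2, the optional MRI is visit 3, and tDCS is visits 4 to 13, ten sessions over two weeks (section 5.3).
- Nominal timing: MRI 1 in week 1, tDCS in weeks 3 and 4, MRI 2 in week 5 (schedule, section 5.2).
- Planned total participation is up to 10 weeks (section 5.4). The MBT phase after tDCS is three weeks (section 5.3).
- 75 people are to be consented, with a minimum target of 30 completers (section 10.1).

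**Step 1. Required tests before the first tDCS session, as written**
- No MRI: 0.
- With MRI: 1, at MRI 1. The MRI 2 test falls in week 5, after all ten sessions, and so cannot stop any of them.

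**Step 2. Age of the one required test when stimulation starts (participants with an MRI)**
- Take week 1 as days 1 to 7 and week 3 as days 15 to 21. The shortest gap is 15 − 7 = 8 days and the longest is 21 − 1 = 20 days, so about one to three weeks.
- If visits slip, the gap can be longer. Within the planned 10 weeks it is at most about 10 − 2 (tDCS) − 3 (later MBT) = 5 weeks.
- The 10 weeks is a planned duration and not an enforced window. Section 5.3 allows for a delay of a month or more, after which repeating baseline visits is discretionary.

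**Step 3. What covers a participant without an MRI**
- Safeguards stated for her are the exclusion criterion, counselling at consent with encouragement to use birth control, self-report of concern, and offered tests.
- The pre-enrolment screen (section 8.3) and the baseline tDCS safety screen (section 5.2) may ask about pregnancy, but those forms are not in the documents.
- None of these is a required test. A positive result on an offered test would still stop tDCS.

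**Step 4. With one required strip at the first tDCS visit**
- No MRI: 0 + 1 = 1. With MRI: 1 + 1 = 2.
- Gap from the latest required test to the first session: 0 days for everyone.
- Extra strips: 30 × 1 = 30 at the completion target, and 75 × 1 = 75 if every consented person reached tDCS.

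**Step 5. Number affected**
- MRI uptake is not stated, so the number of women who would go without a required test cannot be computed.

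**The case against.** The best defence is that pregnancy is already handled for everyone. Even a possible pregnancy excludes, the bar on stimulation is unconditional, participants are counselled and asked to report concerns, and a test can be offered at other visits. Section 4.2 classes the device as non-significant risk. Nothing shows that anyone will decline the scan, and nothing in the documents says that a pregnancy exclusion must be confirmed by a test. The proposed change also accepts self-report and offered tests for sessions 2 to 10, so the disagreement comes down to one check at the start of treatment.

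Most of this stands, and it limits the weight of the point. It does not remove it. Each safeguard for a participant without an MRI depends on her suspecting a pregnancy or on staff choosing to offer a test, whereas the plan does not rely on that for a participant with an MRI. The MRI subsection does contain a line saying that all participants are scanned at baseline, but the same paragraph makes the scan optional, so that line does not close the gap.

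Two stronger inferences are tempting, and the documents support neither. A reader might conclude that the plan permits stimulation of a pregnant participant who skips the scan. It does not: the bar and the stopping rule apply to her too, and only the required verification is missing. A reader might also conclude that the interval between the baseline MRI test and tDCS is unlimited, because repeat baseline visits are discretionary. The planned duration of up to 10 weeks puts it at about five weeks at most if that plan is kept.

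**Conclusion.** The point holds as a modest gap in verification. Before ten tDCS sessions that section 13.2 denies to pregnant participants, the plan requires 0 tests of a participant without an MRI and 1 of a participant with one, the latter nominally one to three weeks old at the first session. This rests on reading the single pregnancy-test mark in the schedule as belonging to the MRI column, which agrees with the text of section 13.2, and on counting only tests stated as required. How much weaker the protection is in practice cannot be judged, because MRI uptake is not given and the screening forms are not reproduced. No statistical analysis is affected. The change is worth making because it is cheap and makes the sponsor's own rule checkable for everyone who is stimulated.

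**What to change.** In section 13.2 and the schedule of activities, require the urine strip already named there from every participant at the first tDCS visit, before stimulation begins, whether or not she has an MRI. Keep the tests before each MRI. Amend the sentence that places testing at the CMRR so that it can also be done where tDCS is given (the Neuromodulation Laboratory or the CNBD, section 23.1), and record the result on a form not tied to the scan. Offered tests and self-report would continue to cover the later sessions.

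The drafting cost is one schedule entry, a few sentences in section 13.2, one CRF field and a small consent and assent update. The running cost is about 30 to 75 extra strips of a test that already has a CLIA waiver, plus urine collection and disposal at the tDCS site. The main downside is an occasional false positive, at a rate the documents do not give, which could stop tDCS for a participant who is not pregnant.
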